**Sponsor:**

**Qatar National Priority Research Program**

**NPRP No.: NPRP 5 - 117 - 3 - 028**

## **1. Introduction and Purpose:**

Our long-term goal is to provide a convenient, low-cost therapeutic device and treatment protocol for diabetic patients with high risk of falling. Eventually, we plan for this to be an approach that can be used by patients at home. We will use preliminary data from this study to plan and implement a randomized clinical study in high risk diabetics to evaluate long-term clinical outcomes, specifically a reduction of falls, foot ulcers and amputations in patients that use the electrical stimulation treatment.

This study will be a double-blind randomized clinical trial design consisting of two groups of forty (40) patients with diabetic peripheral neuropathy and some level of postural instability. The study consists of a 12 weeks treatment phase and two weeks of retention. Subjects will be asked to wear a comfortable electrical stimulation device (SENSUS™ Pain Management System, Neurometrix, Inc., Waltham, MA) during night time on daily basis for duration of 8 hours. The proposed dosage regimen was used in our preliminary studies and no related adverse event was reported while a significant improvement in skin perfusion was observed. The objective of this proposed study is threefold:

**Aim1:** To compare postural control in subjects assigned to use the active Electrical Stimulation (intervention group) and subjects assigned to non-functional stimulator (sham group). Balance will be assessed for both groups at baseline and at monthly intervals. Study hypotheses are:

**H1:** Electrical Stimulation will improve postural coordination and helps to reduce body sway during standing in the treatment group compared to the sham group as well as compared to the baseline.

**H2:** Electrical Stimulation will improve gait, gait initiation, and gait inter-cycle variability compared to the sham group as well as compared to the baseline.

**Aim2:** To compare changes in skin perfusion in patients treated with Electrical Stimulation compared to sham therapy.

**H3:** Electrical Stimulation will improve dorsal and plantar perfusion compared to the control group and compared to baseline.

**Aim3:** To evaluate changes in quality of life in high risk diabetes who received Electrical Stimulation compared to sham therapy.

**H4:** Plantar stimulation will improve subject quality of life in the intervention group assessed using SF36.

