To examine postural compensatory strategy, we will use RCI (reciprocal compensatory index) introduced in our previous study-see preliminary study #1(Najafi, Horn et al. 2010). This index represents how the movement around ankle joint is compensated by the reciprocal movement around hip joint to reduce the variation of COM. (Najafi, Horn et al. 2010) By comparing the balance control and postural compensatory strategy between DPN and control group, we will explore whether and how neuropathy may impact balance and during which conditions (e.g. closing eyes ). The data is coded so the investigators involved in the data analysis are blind to the subject group (i.e. Sham v. Intervention group). We assumed at baseline there is no significant difference for the static postural control between two groups. But during treatment, balance will be significantly improved in the intervention group while it will be deteriorated or remained the same in the sham group (Hypothesis 1).

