### **14. Biostatistics:**

**Power & Sample Size Estimation:** The sample size for the study was designed to achieve 85% power when comparing the change in the actively treated group to the change in the sham treated group, using assumed rates of 50% and 10% improvement, respectively. A two-sided test of results in evaluable subjects (qualified for analyses of efficacy on vibration perception threshold and on structured S-W monofilament testing) will provide the specified power at a 5% significance level. Sample size calculations resulted in a requirement for a total of twenty-seven (27) subjects in each group. The sample size was also estimated using our pilot data in which we explored the benefit of plantar stimulation for improving balance (Study 5). At baseline, the area of sway for center of mass (COM) was  $5.23 \pm 2.81 \text{ cm}^2$  and  $5.41 \pm 1.14 \text{ cm}^2$  respectively for the sham and intervention groups. After week two of treatment, the area of COM sway was  $4.94 \pm 3.42 \text{ cm}^2$  for the sham and  $3.49 \pm 1.25 \text{ cm}^2$  for the intervention group. Using the same criteria explained above, to observe a significant improvement in the intervention group receiving active stimulation compared to sham group (with nonfunctional stimulator), twenty seven subjects per group is required. Assuming 10% drop out, therefore, 40 subjects per group (a total of 80 subjects) should be enough for the purpose of this study.

No suitable alternative treatments exist for patients with loss of protective sensation due to diabetic peripheral neuropathy, so a statistically detected difference in improvement between groups may be considered a clinically meaningful result. However, the study was designed to detect a sufficiently large difference to account for an anticipated “placebo effect” in the sham treated group.

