### **Analysis Plan:**

P-values of 0.05 or less will be considered statistically significant based on a two-sided test unless otherwise noted. All variables will be tabulated descriptively at each scheduled time point. For each continuous variable, the analyses will include the mean, standard deviation, minimum and maximum. For each categorical variable, the summary will include frequencies and percentages. Each variable will be analyzed using all available data. Baseline variables will be summarized using descriptive statistics. Between-group differences for primary and secondary endpoints will be explored at the time of the last treatment visit (weeks 12) and every two weeks of treatment.

Additionally, the retention of potential benefit will be assessed at the time of follow-up visit following the completion of treatment (two weeks post termination of treatment). The frequency of subjects

with adverse events (AEs) will be tabulated. AEs will also be tabulated by severity and, when appropriate, by relationship to study treatment. The difference in the occurrence of adverse events between the study groups will be compared descriptively.

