To determine whether gait, balance, and physical activity variables change significantly across different study visit epochs, within-subject analyses of variance (ANOVA's) will be employed. We assume that plantar electrical stimulation is helpful to improve subjects gait, balance, and physical activity. Then sensor-derived movement variables should change substantially from baseline to the end of the study for the active group with no significant change in placebo group. For example, the range of motion of COM and RCI values should be reduced and gait velocity should be increased. Next, for all continuous variables, pretreatment scores will be regressed on post-treatment scores to form residualized change scores (e.g. VPT, monofilament test, pain intensity, A1C, etc). Correlations will then be generated among these scores to determine whether changes in sensor-derived movement factors are related appropriately with increases in (clinically assessed) functional capacities and self-report measures of activities, mood, socializing, etc. ANOVA test will be used to examine significant difference between intervention and sham group at baseline for age and BMI as well as the indicated outcomes (e.g. gait, balance, VPT, ABI,. Etc). We assumed there is no significant difference between sham and intervention group at baseline for the indicated variables. The same test will be repeated for the week 12. We assumed that the outcomes of study will be improved in the intervention group compared to the sham group. Paired- sample t-test will be used to examine the retention of the electrical stimulation therapy at two weeks post stopping the therapy compared to week-12. We assumed the benefit of the electrical stimulation therapy will be retained at least for two weeks. Additional analyses will examine the degree to which early-treatment changes in cognitive variables and functional capacity variables (representing functional restoration processes) predict late-treatment changes in moving ability post plantar electrical stimulation therapy. Such analyses will also allows to elucidate the relative contributions fear of falling (assessed using FES score); and/or and range of motion (assessed using body worn sensors) made to bringing about clinically meaningful changes in gait balance control. Moderator effects will also be examined for exploratory purposes. Using gender as an example, mixed design ANOVA's will be conducted to determine whether gait and balance factors change over the course of treatment at different rates or with different patterns for men and women as well as for patients with high or low severity of neuropathy and peripheral vascular disease. We assume those who have higher peripheral vascular problem will receive maximum benefit from electrical stimulation. Additional analyses will test whether changes in gait and balance variables predict changes in clinically important outcome factors (e.g., fear of falling (FES) , quality of life (SF12), adverse events, foot ulcer, etc) depending on gender.

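### The plan sets a within-arm significance pattern beside an active-versus-sham test without saying which decides benefit

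*Combined protocol and SAP*

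**What the plan says.** **Within-arm side.** For change across visits in gait, balance and physical activity, the Analysis Plan (section 14) names a within-subject ANOVA. It then gives the expected result: sensor-derived variables "should change substantially from baseline to the end of the study for the active group with no significant change in placebo group". The text under Specific Aim 1, after Table IV, expects the same pattern for Hypothesis 1: "balance will be significantly improved in the intervention group while it will be deteriorated or remained the same in the sham group". In section 1, H1 to H3 each claim improvement against baseline in addition to sham or control. H4 reads "Plantar stimulation will improve subject quality of life in the intervention group assessed using SF36". H5 also names no comparator, and the restatements of H4 and H5 under Specific Aim 3 add none.

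**Between-arm side.** The Analysis Plan says group differences will be explored at the last treatment visit, given as week 12, and every two weeks. It applies an ANOVA of intervention versus sham at baseline and repeats it at week 12, expecting improvement relative to sham. The sample size was set to "achieve 85% power when comparing the change in the actively treated group to the change in the sham treated group". Aim 3, which contains H4 to H6, is framed against sham therapy, and H6 as restated under Specific Aim 3 names sham as well as baseline.

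**Placebo response.** Section 14 states that "the study was designed to detect a sufficiently large difference to account for an anticipated" placebo effect in the sham arm.

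**Significance.** "P-values of 0.05 or less will be considered statistically significant based on a two-sided test unless otherwise noted".

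Nothing ranks these analyses. Mixed-design ANOVA is named only for moderators such as gender and disease severity, not for arm by visit.

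**The concern.** A non-significant test in the sham arm does not show that sham did not change, and comparing two p-values does not compare two changes. Suppose both arms improve by the same amount, because participants respond to wearing a device or become practised at tests repeated at every visit. Then chance alone will often put one arm below 0.05 and leave the other above it. When the arm below is the active one, the data match the pattern that the plan describes as its expectation.

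The randomised sham arm is there to remove exactly this shared change. If the within-arm pattern, or a baseline-only reading of H4 or H5, may count as support, that protection is lost for the claim concerned. With no order of precedence, a report could rest on whichever result is favourable.

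**Working it through.** **1. The plan's own figure.** Section 14 gives 85% power, "using assumed rates of 50% and 10% improvement, respectively", and a "requirement for a total of twenty-seven (27) subjects in each group". Read as a comparison of two proportions, with z = 1.960 and 1.036 and mean proportion 0.30:

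- Uncorrected: n = [1.960·√(2·0.30·0.70) + 1.036·√(0.50·0.50 + 0.10·0.90)]² / 0.40² = 21.96, so 22.
- Continuity-corrected: (21.96/4)·[1 + √(1 + 4/(21.96·0.40))]² = 26.7, so 27.

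The stated 27 reproduces, and it rests on a comparison between arms.

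**2. Inputs for the error rate.**

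- From section 14: two-sided 0.05; 40 per arm less 10% dropout, 40 × 0.90 = 36.
- Assumed: the same true change *d* in both arms, in units of the SD of the change score; independent arms; normal change scores. A paired t-test of baseline against end stands in for the multi-visit within-subject ANOVA. The documents give neither *d* nor the SD of change.

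**3. Rate of the pattern when stimulation adds nothing.** Let p be the power of the within-arm test, from the non-central t with 35 degrees of freedom and non-centrality d·√36. With equal variances, P(active significant, sham not) = p(1 − p).

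| Shared change d | p | p(1 − p) |
|---|---|---|
| 0.20 | 0.21 | 17% |
| 0.33 | 0.49 | 25% |
| 0.40 | 0.65 | 23% |
| 0.50 | 0.83 | 14% |

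The product cannot exceed 0.25, reached when p = 0.5. With no shared change the rate is 2.4%. At 27 per arm it is 14% at 0.2 SD, and the 25% peak falls at 0.39 SD.

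**4. The direct test.** Simulating an equal change in both arms at 27 per arm (200,000 replicates), the between-arm test of change is significant in 4.9% to 5.0% of trials, about 2.5% favouring active, whatever the size of the shared change. Requiring both the pattern and a favourable between-arm result gives at most about 2.4%.

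**5. A hypothesis read against baseline only.** The false-claim rate is then p itself: about 49% at 0.33 SD with 36 per arm. The 25% maximum does not apply.

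**6. Pilot figures.** Sham sway fell from 5.23 to 4.94 cm², a change of 0.29 cm² (0.29/5.23 = 5.5%). SDs at baseline and week 2 were 2.81 and 3.42 (sham) and 1.14 and 1.25 (active). The pre-post correlation r is not given; I assume 0.3 to 0.7. SD of change = √(SD₁² + SD₂² − 2r·SD₁·SD₂), which gives 3.72 to 2.48 for sham and 1.42 to 0.93 for active. At 36 per arm, for a shared change of 0.29 cm²:

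- Sham SD used for both arms (d = 0.08 to 0.12): about 6% to 9%.
- Each arm's own SD: about 21% to 40% (16% to 31% at 27 per arm).

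At the least favourable shared change, the unequal-SD rate at 27 per arm reaches about 69%.

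**The case against.** The best defence is that the plan is not a within-arm plan. The sample size rests on change in active against change in sham, the Analysis Plan states its between-group comparisons before it mentions the within-subject ANOVA, and the week-12 ANOVA compares the arms directly. The sentence about no significant change in the placebo group is introduced as an assumption, not as a criterion for efficacy. H4 and H5 sit under an aim framed against sham. All of this stands.

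Four stronger readings are therefore not supported:

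- A reader might infer that the plan judges benefit by the within-arm pattern alone and so errs in a quarter of its tests. The between-arm analyses are planned, and 25% is an equal-variance maximum that arises only where the pattern is used as evidence.
- A reader might infer that a true effect would be rejected if sham improved significantly. No such rule is written.
- A reader might see a contradiction between the 10% sham improvement in section 14 and the expectation of no sham improvement under Specific Aim 1. The 10% is tied to subjects evaluable on vibration perception and monofilament testing; the other statement concerns static balance.
- A reader might take the end of the study to be the visit two weeks after treatment stops. The phrase is undefined, and the plan already gives that visit its own retention test.

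What the defence does not supply is precedence. Between-group differences are to be explored with no test named there, the named ANOVA compares the arms at week 12 rather than their changes, and no arm-by-visit test of treatment appears. That ANOVA also lacks a matching visit: sections 1 and 14 give 12 weeks of treatment, while section 4 and Table IV schedule treatment visits to week 6 and a last visit at week 8. Those sections must be reconciled.

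**Conclusion.** The concern holds as a gap in the decision rule: two kinds of evidence stand side by side, one of them invalid for a treatment effect, and neither is named as decisive. Where the within-arm pattern is used, an equal change in both arms produces it in about 14% to 25% of tests at 36 per arm for a shared change of 0.2 to 0.5 SD. Smaller or larger shared changes give lower rates, and unequal variances can give higher ones. The between-arm test holds about 5% two-sided.

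These sizes depend on the assumed shared change, on the paired test as an approximation and, for the pilot-based figures, on an assumed correlation. That comparing significance between arms is invalid depends on none of them. Because valid between-arm comparisons are already planned, this is a should-fix point rather than a fundamental failure of the design.

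**What to change.** - State that H1 to H6 are supported only by one active-versus-sham contrast of on-treatment change: either an arm-by-visit term or a baseline-adjusted comparison at the last treatment visit.
- Report within-arm changes descriptively with confidence intervals.
- Remove the absence of significant change in the placebo arm as a criterion in the Analysis Plan.
- Add the comparison with sham to H4 and H5, in section 1 and under Specific Aim 3.
- State that the post-treatment visit serves the retention question only.

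The cost is wording in the Analysis Plan and the hypotheses, with no new data, and the analysis would then match the change-versus-change basis of the sample size. The downside is that improvement against baseline can no longer be claimed as efficacy.

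### The residualising regression is stated in the wrong direction (pretreatment on post-treatment), so, followed literally, the supportive change-score correlations carry baseline association

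*Combined protocol and SAP*

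**What the plan says.** Section 14 (Biostatistics), Analysis Plan, describes this step after the within-subject ANOVAs. It applies to every continuous variable: "pretreatment scores will be regressed on post-treatment scores to form residualized change scores". Vibration perception threshold, monofilament testing, pain intensity and A1C are among the examples. The scores are then used together: "Correlations will then be generated among these scores to determine whether changes in sensor-derived movement factors are related appropriately with increases in" clinically assessed functional capacity and self-report measures.

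The plan gives no formula or model statement for the scores, and no other section restates or corrects the direction. The sentence also does not say which visit supplies the post-treatment value.

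The group comparison is a separate step. Baseline outcomes are compared between arms by ANOVA, and "The same test will be repeated for the week 12". The general significance rule is "P-values of 0.05 or less will be considered statistically significant based on a two-sided test".

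**The concern.** In ordinary usage, regressing Y on X makes Y the outcome. The sentence therefore defines the score as the pretreatment value minus what the post-treatment value predicts. A residualised change score is the reverse: the post-treatment value minus what baseline predicts. Its purpose is to remove baseline, so that patients who started at different levels can be compared on how far they moved.

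The reversed residual removes the post-treatment value and leaves baseline in. Sensor and clinical measures of the same neuropathy may well be correlated before treatment. If they are, correlating reversed scores carries some of that baseline association into what is reported as an association between changes. At stake is the plan's claim that sensor-measured movement changes go along with clinical and self-reported changes. An analyst who programs the sentence as written would get plausible-looking output with nothing to signal the problem.

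**Working it through.** The plan states no figure on this point, so there is none to reproduce. The check is algebra plus simulation.

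**Inputs from the documents**
- Direction of the regression, its application to all continuous variables, and the use of the scores in pairwise correlations: section 14, Analysis Plan.
- Two-sided 5% level: same place.
- 80 enrolled and 10% dropout, so 80 × 0.9 = 72 patients; 27 evaluable per group, so 54: section 14, sample size paragraph.

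**Assumptions (not in the documents)**
- Standardised scores with equal pre and post variances, and the same pre-post correlation r for both variables.
- c = correlation of the two variables at baseline; k = correlation of their baseline-adjusted changes.
- r is varied from 0.5 to 0.9.

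**One score.** Write post = r·pre + e, with var(e) = 1−r². The literal score is U = pre − r·post = (1−r²)·pre − r·e, and var(U) = (1−r²)² + r²(1−r²) = 1−r².
- Correlation of U with post: 0.
- Correlation of U with baseline: √(1−r²).
- Correlation of U with raw change (post − pre): −√((1+r)/2).
- Share of the variance of U due to baseline: 1−r².

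| r | with baseline | with raw change | baseline share |
|---|---|---|---|
| 0.5 | 0.87 | −0.87 | 75% |
| 0.7 | 0.71 | −0.92 | 51% |
| 0.8 | 0.60 | −0.95 | 36% |
| 0.9 | 0.44 | −0.97 | 19% |

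**Two scores.** The covariance of two literal scores is (1−r²)²c + r²(1−r²)k. Dividing by 1−r² gives

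correlation = (1−r²)c + r²k.

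The conventional scores give k.

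| r | c = 0.5, k = 0 | c = 0, k = 0.5 | c = k = 0.5 |
|---|---|---|---|
| 0.5 | 0.75 × 0.5 = 0.38 | 0.25 × 0.5 = 0.13 | 0.50 |
| 0.7 | 0.51 × 0.5 = 0.26 | 0.49 × 0.5 = 0.25 | 0.50 |
| 0.8 | 0.36 × 0.5 = 0.18 | 0.64 × 0.5 = 0.32 | 0.50 |
| 0.9 | 0.19 × 0.5 = 0.10 | 0.81 × 0.5 = 0.41 | 0.50 |

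Simulation with 400,000 draws agreed with the formula to within 0.005.

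**False positives when c = 0.5 and k = 0**
- n = 72, Fisher z. At r = 0.5, atanh(0.375) × √69 = 3.27, and Φ(3.27 − 1.96) ≈ 91%. The same step gives 58% at r = 0.7 and 33% at r = 0.8.
- n = 80, 4,000 simulated trials: 94%, 62%, 35% and 12% at r = 0.5, 0.7, 0.8 and 0.9.
- n = 54, 4,000 simulated trials: 80%, 45%, 24% and 10%.
- Conventional scores at n = 80: 4–5% throughout.

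**The case against.** **It may be a slip of wording.** The sentence names its product with a term that has a standard construction, and many analysts would build the conventional score whatever the verb order. That is plausible, but the text does not settle it. The finding is therefore about the written instruction and what follows if it is obeyed, not about what the trial team will do.

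**Sign.** A reader might infer that every planned correlation would come out reversed. The plan expects that "the range of motion of COM and RCI values should be reduced and gait velocity should be increased", and under the literal score a patient whose sway falls does get a higher value. But the plan builds every score the same way and correlates the scores with each other, so the two flips cancel. The sign can still be wrong through baseline contamination: c = 0.5, k = −0.3, r = 0.5 gives 0.375 − 0.075 = +0.30. A systematic flip needs a reversed score paired with a conventional one, where the correlation is −rk (−0.35 at r = 0.7, k = 0.5). The plan does not specify such a pairing.

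**Mostly baseline.** A reader might also infer that the scores mainly measure baseline level. That holds only for r below about 0.71. Once r exceeds 0.5, the literal score correlates more strongly with raw change than with baseline. The documents give no pre-post correlation.

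**One-sided scenario.** The false-positive figures assume a baseline correlation and no link between changes. With c = k there is no bias, and with c = 0 a real link is understated. This stands: the direction of the bias is unknown.

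**Reach.** The hypotheses in section 1 are comparisons with sham or baseline, or predicted improvements, and the tests for these do not use the scores. This also stands.

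**Conclusion.** The regression is wrong as written. Followed literally, it gives scores that are not free of baseline, and correlations among them do not in general estimate the association of baseline-adjusted changes. The fault is baseline contamination.

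Its size depends on r, c and k, all assumed here. It can be large: false-positive rates of about 33% to 91% at n = 72 for r from 0.8 down to 0.5, with c = 0.5 and k = 0. It can also be nil (c = k), or a loss of a real association.

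The documents do not support extending the point to the efficacy results. The week-12 between-group ANOVA, the within-subject ANOVAs and the paired t-test for retention do not use these scores. The damage is confined to the supportive correlation analysis, and the error should be corrected before that analysis is programmed.

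**What to change.** Reverse the regression in that sentence of the Analysis Plan: for each continuous variable, regress the post-treatment score on the pretreatment score, and use the residual (observed minus predicted post-treatment score) as the residualised change score. Under the model above, this score is uncorrelated with baseline, and the correlation of two such scores recovers k. While the sentence is open, name the visit that supplies the post-treatment value.

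No treatment-arm term is needed to correct the direction. Adding one would change what the correlation estimates, by removing between-arm differences in change, and would need its own justification.

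The cost is one sentence. It needs no new data, no extra visits and no change to the sample size.

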**Figure 9** Aqueous treatment of DPN using stimulator plantar stimulation technology significantly improved postural control in Active group compared to baseline as well as sham group.

**Figure 10** Patients with poor hyperglycemia control (higher A1C level) has weaker postural control

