#### **Table IV: Clinical Assessments**

QNPRP Protocol

Version 3 – 12 Oct 2015

Page 12 of 23

Baseline	
Medical History: This will include: duration and type of diabetes, type of diabetes medication (insulin, oral, combination therapy, diet), previous history of foot ulcers, previous history of falls, amputation (toe, foot), lower extremity bypass, lower extremity angioplasty, Coronary artery bypass surgery, cardiac angioplasty, arthritis, liver disease, osteoporosis, malignancy, and bone tumors. We will use the Kaplan co-morbidity index to record disease severity. We will use the New York Heart Association criteria to classify congestive heart failure, and the National Kidney Foundation Disease Outcomes Quality Initiative Clinical Practice Guidelines for chronic kidney disease to stage kidney disease. We will document all prescription and over-the-counter medications. We will measure height and weight to determine body mass index (BMI). We will record prescription and over-the-counter medications.

Baseline	
Social Factors: We will evaluate the following factors: marital status, years of education, type of work, tobacco history (pack years, current smoker, current use of chewing tobacco, previous smoker, no tobacco history), drug history (current, previous history, no drug history), education, occupation, and alcohol history.
 
Foot questionnaire and foot exam

Baseline Questionnaires	
Screening Test for frailty assessment: Fried Frailty Criteria: Weight loss >10 pounds in preceding year; Grip strength; Low levels of physical activity; 15 foot walk time; Exhaustion[13]
 
* Screening for cognitive problem: Folstein Mini-Mental State Exam score [15]
 
* Foot questionnaire and foot exam
 
* Barthel ADL Index
 
* Depression Assessment
 
* Fear of Falling Scale
 
* Mobility Tiredness Scale
 
* Pain Assessment Scale
 
* SF-12 (at baseline and 6 week time points)

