## 7. Criteria for Exclusion of Subjects:

Exclusion
Amputation and active ulcers or infection
Cognitive deficits. MMSE score of 24 or lower
Unable to stand for more than 5 minutes (including symptomatic orthostatic hypotension or pain)
Any clinically significant orthopedic, muscular, or peripheral vascular disorders that affect
Alcohol or substance abuse within 6 months or major psychiatric disorder.
Significant vision problem Less than 20/100 vision after correction
Any other neurological or medical disorders that may significantly affect balance based on clinical judgment (e.g. CVA, asymmetric)
Refusing or lacking medical decisional capacity to provide informed consent.
Use of medications that is likely to affect cognition or balance (based on physician review) within 14 days

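### The analysis plan uses change in A1C, cognition, mood and fear of falling, but Table IV schedules no A1C and lists the MMSE, depression and fear-of-falling scales at baseline only.

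*Combined protocol and SAP*

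**What the plan says.** The Analysis Plan (section 14) describes three linked analyses. First, for all continuous variables, it regresses the values before treatment on those after it to obtain "residualized change scores (e.g. VPT, monofilament test, pain intensity, A1C, etc". Second, these scores are correlated, to see whether changes in the sensor measures go along with gains in "functional capacities and self-report measures of activities, mood, socializing, etc". Third, a further analysis asks how well "early-treatment changes in cognitive variables and functional capacity variables" predict later change in movement; the sentence after it brings in fear of falling (FES) and sensor range of motion as contributors.

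Table IV sets out what is collected. Its Baseline Questionnaires row contains "Screening for cognitive problem: Folstein Mini-Mental State Exam score", the "Depression Assessment", the Barthel index, the Fear of Falling Scale, the Mobility Tiredness Scale, a pain scale and the SF-12. Only the SF-12 entry gives a second time point, week 6. The rows repeated every two weeks hold the neuropathy tests, pain VAS, gait, balance and vascular measurements. A1C is in no row of Table IV and is not listed in section 8 (Sources of Research Material). The MMSE also serves as an entry criterion in section 7: "MMSE score of 24 or lower" is an exclusion.

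Hypothesis 6, under Specific Aim 3, expects fear of falling to improve against baseline and against sham, measured with the FES.

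**The concern.** A change score needs a baseline value and a later value from the same patient. An early-treatment predictor needs a value taken early in treatment. The Analysis Plan names or implies variables for which the schedule supplies no later value.

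If this stays as it is, some planned analyses will be dropped without comment, or other variables will be substituted after the data are in. Questionnaire answers that were not collected cannot be recovered once patients have finished. For fear of falling the stake is higher, because a stated study hypothesis depends on its change.

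**Working it through.** No sample size, power or alpha figure bears on this point. The check sets the variables in the Analysis Plan against the schedule in section 4, Table IV, the Specific Aims text and section 8.

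Rule for a change score: the residual is y_post − (a + b × y_pre), or the reverse regression as the plan words it. Either way both values are needed, so the number of scores equals the number of patients with both. Rule for an early change: a baseline value plus a value at week 2 or week 4.

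| Variable | Scheduled weeks (0 = baseline) | Occasions | Post-baseline | Change score possible | Early change possible |
|---|---|---|---|---|---|
| A1C | none | 0 | 0 | no | no |
| MMSE | 0 | 1 | 0 | no | no |
| Depression Assessment | 0 | 1 | 0 | no | no |
| Fear of Falling Scale | 0 | 1 | 0 | no | no |
| Barthel index, Mobility Tiredness (each) | 0 | 1 | 0 | no | no |
| SF-12 | 0, 6 | 2 | 1 | yes | no |
| VPT, monofilament, pain VAS, gait, balance (each) | 0, 2, 4, 6, 8 | 5 | 4 | yes | yes |

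The three analyses in turn:

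1. *Residualized change scores.* Of the four examples in the plan's list, VPT, monofilament and pain can be formed; A1C cannot.
2. *Correlation with mood and activities.* The depression scale gives no change. SF-12 gives one, from baseline to week 6, but the plan does not name it for this purpose.
3. *Early predictors.* If the cognitive variables mean the MMSE, no early change exists. If functional capacity means the gait or balance tests, that part can run, because both are measured at weeks 2 and 4. SF-12 cannot be an early predictor.

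Two features of the documents make it unlikely that repeats were intended but left unwritten. SF-12 shares a row with the MMSE and depression scale and carries its own second time point, so a repeat was marked where one was meant. Section 4 independently describes the clinical assessments repeated at each visit as those for neuropathy severity and skin perfusion.

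**The case against.** The strongest reply is that little is broken. A1C is one item in a list of examples, and the change-score analysis runs for most of what the plan names. The mood correlation needs only a before and an after value, which SF-12 has. The plan never names the Barthel index or the Mobility Tiredness Scale, and functional capacity is undefined and may mean the repeated gait and balance tests. The cognitive variables may not be the MMSE: the next sentence turns to fear of falling, and the gait test includes a walk with a counting task at every visit. The analyses are correlational or additional, and the comparison of the arms does not use change in A1C, MMSE or depression.

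Most of this stands. A reader might infer that the change-score, mood and predictor analyses cannot be run at all; the documents do not support that. The reply does not rescue A1C change, MMSE change or depression change. Reading the cognitive variables as fear of falling moves the gap without closing it, because that scale is also baseline-only. The counting-task walk is repeated, but the plan would have to name it.

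A reader might also infer from the Figure 10 caption, "Patients with poor hyperglycemia control (higher A1C level) has weaker postural control", that a needed adjustment variable is lost. That does not follow. The Analysis Plan specifies no covariate-adjusted comparison of the arms, the figure is not shown, and Study 5 assessed balance in only thirteen subjects. Table IV does allow patient records to be gathered if available, but it names history and examinations, not laboratory results, and it schedules no pair of A1C values. Nor should one argue that the MMSE entry cut-off leaves too little room for change: the documents do not give the scale's maximum, and without a second MMSE the range does not matter.

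**Conclusion.** The point holds as a contradiction between the analysis plan and the visit schedule. Scheduled change scores number 0 of 80 patients for each of A1C, MMSE and depression, and there is no early change in MMSE. VPT, monofilament, pain VAS, gait and balance are unaffected, and SF-12 supports a single change to week 6.

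For A1C, cognition and mood the consequence is limited to secondary correlational and predictor analyses; none of the six hypotheses depends on them. Fear of falling is different. With a baseline value only, the fear part of Hypothesis 6 can be tested neither against baseline nor against sham, and the FES contribution in the Analysis Plan cannot be estimated.

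The assumptions are that Table IV is the full schedule, that its Fear of Falling Scale is the FES of Hypothesis 6 (if it is a different scale, the FES is not in Table IV at all), and that the cognitive variables are the MMSE unless the plan defines them otherwise. The documents also differ on when treatment ends: week 6 in section 4, week 12 in section 1 and the Analysis Plan. Those passages must be reconciled before the end-of-treatment visit can be fixed. The counts above do not depend on the answer, but whether the week-6 SF-12 is an end-of-treatment value does.

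**What to change.** In the Analysis Plan:

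- Remove A1C from the list of change-score variables.
- Remove the cognitive variables from the predictor analysis, or define them as a named measure that Table IV repeats.
- Define functional capacity, and limit early predictors to variables measured at week 2 or week 4.
- If SF-12 is to be the self-report measure for mood and social function, name it, and state that it gives one change, from baseline to week 6.

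In Table IV:

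- Repeat the Fear of Falling Scale at the end-of-treatment visit, and also at week 2 or week 4 if it is to be an early predictor. It should not be dropped, because Hypothesis 6 needs it. Use one name for the scale in Table IV and Hypothesis 6.
- If change in mood or daily function is wanted beyond SF-12, repeat the depression and function questionnaires at the end-of-treatment visit.

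The Analysis Plan changes cost wording only. The repeats cost a few minutes of questionnaires per patient at visits that already take place. They must be in place before patients reach those visits.
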